9. Through injection intravenous drug use	True	False
10. Sharing cigarettes, food, or drink	True	False
11. An HIV-infected pregnant women infecting her baby	True	False
12. You can tell someone has HIV by looking at them	True	False
13. As long as I'm tested I'm safe	True	False
14. The medication used to treat HIV	True	False
15. HIV tests	True	False
HIV is prevented by:		
1. Using condoms	True	False
HIV is caused by:		
2. A virus	True	False
3. Spiritual forces	True	False

ART Knowledge and Attitudes

Are you worried about: Responses are 1 Not at all, 2 A little, 3 Somewhat, 4 Very

1. ART side effects? _____
2. ART ineffectiveness? _____
3. Having to take ART? _____
4. Friends finding out you are on ART? _____
5. Family finding out you are on ART? _____
6. Your sexual partner finding out you are on ART? _____

Do you agree or disagree: Responses are 1 Agree, 2 Disagree

7. ART prevent mother-to-child HIV transmission_____
8. HIV can be prevented by ART after rape_____
9. HIV can be controlled by ART_____

10. HIV can be cured by ART _____
11. Taking ART prevents disease progression _____
12. Not starting ART when indicated can make you sick _____
13. Antiretroviral medicine can cause side effects _____

Importance of ART adherence: Responses are 1 Agree, 2 Disagree

14. Taking ART on schedule prevents you from being sick _____
15. Missing doses of ART leads to disease progression _____
16. Missing doses of ART increases risk of transmitting HIV _____

Adolescent Risk Behavior Assessment

In this interview, you will use the headphones to listen to questions and enter your answers into the computer. This will allow you to answer the questions in complete privacy. No one will be able to hear the questions or see the answers you put into the computer. Please be as honest as you can, and take your time to read and listen to each question before answering.
 
These questions ask about your drug use, sexual behavior, and medical health. Please answer EVERY question, but only give ONE answer per question. Remember, these answers are confidential.
		

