1	
By oral sex we mean, have you ever put your mouth on anyone else's penis/vagina or has anyone else put his/her mouth on your vagina/private parts. By vaginal sex, we mean has anyone ever put his penis into your vagina/private part. By anal sex we mean, has anyone ever put his penis in your anus/butt.
 
Have you ever had sexual intercourse of any kind (oral, vaginal or anal)?
	
1= Yes 2= No [Skip]

2	
The very last time you had sex, did you use a condom?
	
1= Yes 2= No

3	
Have you ever had oral sex? (By "oral sex" we mean, have you ever put your mouth on anyone else's vagina/penis or has anyone else put his/her mouth on your vagina/private parts?)
	
1= Yes 2= No [Skip]

4	
In the past 120 days, have you had oral sex (mouth on privates)?
	
1= Yes 2= No [Skip]

5	
In the past 120 days, how many times have you had oral sex (mouth on privates)?
	    (Range 1-999)
6	
In the past 120 days, when you had oral sex (mouth on privates), how many times did you use a condom (rubber) or dental dam?
	    (Range 0-999)
7	
Have you ever had vaginal sex? (By "vaginal sex," we mean when a man puts his penis in a woman's vagina.)
	
1= Yes 2= No

8	
In the past 120 days, have you had vaginal sex (penis in vagina)?
	
1= Yes 2= No [Skip]

9	
In the past 120 days, how many times have you had vaginal sex (penis in vagina)?
	    (Range 1-999)
10	
In the past 120 days, when you had vaginal sex (penis in vagina), how many times did you use a condom ?
	  
11	
Have you ever had anal sex? (By "anal sex," we mean when a man puts his penis in someone's anus or butt.)
	
1= Yes 2= No

12	
In the past 120 days, have you had anal sex (penis in butt)?
	
1= Yes 2= No [Skip]

13	In the past 120 days, how many times have you had anal sex (penis in butt)?	     (Range 1-999)

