32	Have you ever had or been told by a doctor or nurse that you had the following medical condition? Herpes	1= Yes 2= No [Skip]
33		
34	How many times have you been told this?	   (Range 1-99)
35	Have you ever been or gotten someone else pregnant?	1= Yes 2= No [Skip]
36	How many times have you been or gotten someone pregnant?	   (Range 1-99)

		1=Always 2=Almost always 3=Sometimes 4=Almost never 5=Never
37	With that in mind: How often do you practice safe sex?	1=Always 2=Almost always 3=Sometimes 4=Almost never 5=Never
38	During the past 120 days, how often did you use a condom when having sex?	1=Always 2=Almost always 3=Sometimes 4=Almost never 5=Never
39	In the next 120 days, how likely do you think it is that you will practice safe sex?	1=Very sure I will 2=Kind of sure I will 3=Kind of sure I won't 4=Very sure I won't
40	In the past 120 days, did you refuse or avoid having sex?	1= Yes 2= No
41	On a scale of 0-100, at this moment, how IMPORTANT is it that you use condoms when having sex? (Please enter any number 0-100) Please use the following scale to answer this question: 0=Not important at all 50=About as important as the other things I would like to achieve now 100=Most important thing in my life)	
42	On a scale of 0-100, at this moment, how CONFIDENT are you that you will use condoms while having sex? (Please enter any number 0-100) Please use the following scale to answer this question: 0=I do not think I will achieve my goal 50=I have a 50% chance of meeting my goal 100=I think I will definitely meet my goal	
43	Have you ever given sex for money, drugs, or shelter?	1= Yes 2= No
44	In the past 120 days, have you given sex for money, drugs or shelter?	1= Yes 2= No
45	Have you ever purchased or bought sex with money, drugs, or shelter?	1= Yes 2= No
46	In the past 120 days, have you purchased or bought sex with money, drugs or shelter?	1= Yes 2= No
47	In the past 120 days, when you have had vaginal or anal sex, how often were YOU using alcohol, marijuana, or other drugs?	1=Never 2=Less than half the time 3=About half the time 4=More than half the time 5=Always
48	In the past 120 days, when you have had vaginal or anal sex, how often was your PARTNER using alcohol, marijuana, or other drugs?	1=Never 2=Less than half the time 3=About half the time 4=More than half the time 5=Always

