		1=Condoms 2=The Pill 3=A diaphragm 4=A cervical cap 5=Gels, creams, suppositories, or foams 6=Depo Provera 7=Other 8=No birth control methods in the past 90
49	In the past 120 days, which of these methods have you used to prevent pregnancy? (Choose all that apply.)	1=Yes 2=No
50	Have you ever smoked cigarettes?	□□□(Range 1-99)
51	How old were you when you first started smoking cigarettes?	1=Yes 2=No
66	In the last 120 days, have you smoked cigarettes?	□□□(Range 1-99)
67	How many days did you smoke cigarettes in the last 120 days?	1=Yes 2=No
68	Have you ever used alcohol (beer, wine, etc.)?	□□□(Range 1-99)
69	How old were you when you had your first drink of alcohol, other than a few sips?	1=Yes 2=No
70	In the past 120 days, have you ever used alcohol (beer, wine, etc.)?	□□□(Range 1-99)
71	How many days did you use alcohol in the last 120 days?	1=Yes 2=No
72	How many times did you use alcohol in the last MONTH?	□□□(Range 1-99)
73	For the next question, you will need to know what we mean by a "drink." For instance, a drink equals 12 ounces of beer, 1 ounce of liquor (such as whisky, gin, or vodka), or 6 ounces of wine.	none
74	Of the days when you were drinking, about how many drinks did you usually have each day?	□□□(Range 1-99)
75	Of the days when you were drinking, on how many days did you get buzzed or drunk on alcohol?	□□□(Range 1-99)
76	When was the last time you used any alcohol?	1=Within the past week 2=2 weeks ago 3=3-4 weeks 4=More than 4 weeks ago
77	When you drink, how often do you get drunk?	0=Don't drink 1=Stop before getting drunk 2=Almost always stop before getting drunk 3=Stop before getting drunk more than half the time 4=Get drunk more than half the time 5=Usually get drunk

78	How likely is it that you WILL drink alcohol in the future? (pick a number from 1-10)	1=Unlikely 5=Somewhat Likely 10=Very Likely

The following questions are about drugs. By "drugs" we mean street drugs or prescription medications that you took more than was prescribed, or that was not prescribed for you. Remember, do not include drugs that you took only as prescribed.
		
78	Have you ever used any form of marijuana, such as pot, weed, hashish, grass or ganja?	1=Yes 2=No
79	How old were you when you tried marijuana for the first time?	   (Range 1-99)
80	In the last 120 days, have you used any form of marijuana, such as pot, weed, hashish, grass or ganja?	1=Yes 2=No

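### Items 38, 47 and 48 of the risk-behaviour questionnaire assume sex in the past 120 days and, as printed, leave a participant who had none without a true answer

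*Combined protocol and SAP*

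**What the plan says.** The module opens with the instruction "Please answer EVERY question, but only give ONE answer per question". Item 1, "Have you ever had sexual intercourse of any kind (oral, vaginal or anal", is a lifetime question whose No answer carries a skip tag without a printed destination.

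Items 4, 8 and 12 ask about oral, vaginal and anal sex in the past 120 days; item 8, for example, reads "In the past 120 days, have you had vaginal sex (penis in vagina". Each has a skip tag on No and stands directly before the act count and condom count for that type of sex.

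Item 38 asks "During the past 120 days, how often did you use a condom when having sex", with the choices "1=Always 2=Almost always 3=Sometimes 4=Almost never 5=Never". Item 47 asks "In the past 120 days, when you have had vaginal or anal sex, how often were YOU using alcohol, marijuana, or other drugs", with the choices "1=Never 2=Less than half the time 3=About half the time 4=More than half the time 5=Always". Item 48 puts the same question about the partner, with the same choices. None of these three items carries a skip tag.

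Item 49 asks which methods of preventing pregnancy were used in the past 120 days. Its last choice is "8=No birth control methods in the past 90".

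**The concern.** A frequency question about behaviour during sex has no meaning for someone who had no sex in the period. If the form still asks for an answer, 'Never' is the choice that comes nearest to being literally true. On item 38 it is also the answer of someone who had sex and never used a condom. On items 47 and 48 it is the answer of someone who had sex and was never using substances. Inactivity is thus merged with high-risk behaviour on one item and with low-risk behaviour on the other two.

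If the module is repeated at 6 and 12 months, a participant who answers 'Sometimes' (3) at baseline and then has no sex could be recorded at 5. That is a move of 5 − 3 = 2 points towards less condom use, although exposure through sex has stopped. The Executive Summary names secondary HIV transmission as one of the risks that motivate the study, so a descriptive or exploratory report on these items would be of interest to readers.

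**Working it through.** The plan gives no figure for this module, so the check is a trace of the printed routing. Take a participant who has had sex (item 1 = Yes) but none in the past 120 days.

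| Items | Content | What happens |
|---|---|---|
| 1 | Any sex, lifetime | Yes, so the lifetime skip does not apply |
| 4, 8, 12 | Oral, vaginal, anal sex in 120 days | No to each; count items 5–6, 9–10 and 13–14 are passed over |
| 15–19 | Lifetime partners | Applicable, must be asked |
| 20 | Partners in 120 days | Printed range is 1–99, so zero cannot be entered |
| 21, 23 | Male or female partners in 120 days | No; only counts 22 and 24 are passed over |
| 25–37 | Infections, pregnancy, safe sex in general | No printed rule routes this participant past item 38 |
| 38 | Condom frequency in 120 days | Reached; no choice is true |
| 47, 48 | Substance use during sex in 120 days | Reached; no choice is true |

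**Could an earlier skip tag be meant to jump past item 38?** On the printed form this is unlikely, for two reasons. Items 15–19 and the infection and pregnancy items ask about lifetime history and would be lost. Also, no single one of items 4, 8 and 12 establishes inactivity: someone answering No to item 12 may have answered Yes to item 8 and should be asked item 38.

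**Who is affected.**
- Item 38: participants with No to all of items 4, 8 and 12. Item 1 counts oral sex as sex, so item 4 matters here.
- Items 47 and 48: participants with No to both items 8 and 12. This includes those with oral sex only, because the wording covers vaginal or anal sex.
- Participants who have never had sex are probably removed at item 1.

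**Does the module handle non-users elsewhere?** Yes. Items 77, 128, 129 and 131, on drinking and drug use, each have a code for people who do not drink or use, or for not applicable. The three sex-frequency items have none.

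**Size, as an assumption only.** Let q be the share of item 38 respondents who are inactive and answer 'Never' (5), and m the mean among active respondents. The item mean is then (1 − q)·m + 5q, a shift of q × (5 − m). The documents give neither q nor m. For an assumed q of 10% to 40% and m of 2 to 3:
- smallest shift: 0.10 × (5 − 3) = 0.2 point;
- largest shift: 0.40 × (5 − 2) = 1.2 points on the 1–5 scale.

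This range shows only how the shift depends on q and m; it is not an estimate for this trial.

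**Item 49.** The stem covers 120 days and the last choice 90, a gap of 120 − 90 = 30 days. Someone whose only use of a method was 91 to 120 days ago can truthfully tick both that method and the no-method choice.

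**The case against.** **No documented analytic role.** The primary outcomes under Measures are adherence, clinic visits and the laboratory values. The Data Analytic Plan names social support and self-efficacy as examples of secondary outcomes. Figure 5, which describes the rest, is not shown. This stands. A reader might infer that a trial outcome is biased, that power is lost or that an arm difference could be reversed. The documents do not support this: they contain no scoring rule, no planned comparison on these items and no rate of inactivity by arm. Calling 5 on item 38 the worst score is likewise an inference from the code order.

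**Recoverable.** Items 4, 8 and 12 already record recent sex by type, and the counts that follow separate inactivity from unprotected sex. This also stands and limits the harm, provided the analyst uses them. No printed rule says so.

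**Hidden routing.** The questionnaire is computer-administered, skip tags carry no destinations, and a module full of skips cannot mean its answer-everything instruction literally. Parts of the table are also damaged in the text available. Unprinted routing may therefore prevent the problem. The point concerns the printed form, and checking the program would settle it.

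**Transmission.** The overarching hypothesis works through viral suppression, not condom use. That is correct, and it makes these items peripheral.

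**Item 49.** It is tempting to say that item 49 has the same gap. It does not: an inactive participant can truthfully report using no method. Restricting it to people with recent sex would discard valid answers on the Pill or Depo Provera, whose use need not depend on recent sex. Only the 90/120 mismatch remains.

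**Conclusion.** The gap is real on the printed instrument. A participant with lifetime but no recent sex reaches items 38, 47 and 48 with no true answer, and 'Never' places the same state at opposite ends: 5 on item 38 and 1 on items 47 and 48. Participants with only oral sex in the period meet the same gap on items 47 and 48.

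It is a small measurement point in a secondary risk-behaviour module. It does not touch the primary outcomes, and the documents do not allow the bias to be sized. The conclusion assumes that the computer program follows the printed form and that some inactive participants choose 'Never' instead of leaving the item blank. The mismatch of recall periods in item 49 is a separate and minor inconsistency.

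**What to change.** **In the questionnaire.** Show item 38 only if item 4, 8 or 12 is Yes, and items 47 and 48 only if item 8 or 12 is Yes. Alternatively, add the choice 'I did not have sex in the past 120 days' to all three; for items 47 and 48 it should say vaginal or anal sex, to match their wording. If the program already routes this way, print the destinations in Appendix 3.

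**For data already collected.** Set item 38 to not applicable when items 4, 8 and 12 are all No, and items 47 and 48 when items 8 and 12 are both No. Where item 4 was passed over because item 3 (lifetime oral sex) was No, count it as No. Report any sex in the past 120 days as a separate yes/no variable, so that a change in sexual activity stays visible. Write this rule down before any comparison by arm.

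**Item 49.** Make the recall period of the no-method choice match the 120-day stem. Do not make the item conditional on recent sex.

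**Cost.** One routing rule or answer choice, one corrected number and a few lines of recoding. The small downside is that items 38, 47 and 48 are analysed in fewer participants.

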cognitive or medical limitations per clinician report, (5) possess a cellphone, and (6) able to give consent. *Adolescents living with HIV (ALH) between the ages 12-17 will also be eligible to participate in focus groups and cognitive interviews as part of a separate component of the Development Phase. Their eligibility criteria is as follows:* (1) *read English and speak English or a local language spoken by clinic staff (e.g., Twi),* (2) *in medical care for HIV and receiving ART at our clinic,* (3) *aware of their HIV status as per parent/guardian report,* (4) *not impaired by cognitive or medical limitations per clinician report,* (6) *able to give assent, and* (7) *their parent/guardian is able to give consent. Parents or guardians of ALH are also able to participate in focus groups and cognitive interviews as part of this separate component. Parent eligibility is as follows:* (1) *speak English or a local language spoken by clinic staff (e.g., Twi),* (2) *own a mobile phone,* (3) *aware of their child's HIV status,* (4) *not impaired by cognitive or medical limitations per clinician report, and* (6) *able to give consent.* Participants in the randomized pilot must have also demonstrated a recent detectable viral load. Study staff will NOT make changes to ART regimens and participants will be encouraged to speak with their doctor if they have concerns about their medications or side effects of these medications. Any unexpected ethical issues that arise with our participants will be discussed immediately with the PI. All participants will receive a resource packet including information on ART as well as references to local health and social services. We will also encourage participants to identify a treatment monitor to take part in the game. This will not be a requirement for our study, however, because those who begin playing the game without a monitor will be incentivized via game rewards to recruit one (and we will assess this occurrence). Participants without a monitor will be assigned a peer educator to fill this role. Inclusion criteria for treatment monitors includes: 1) *read English and speak English or a local language spoken by clinic staff,* (2) *target HIV patient has agreed to their participation,* (3) *aware of target patient's HIV status as per patient report,* (5) *possess a cellphone, and* (6) *able to give consent.*

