Design Considerations. Mobile phones—access and confidentiality. Participants will need their own phones to enroll in the study. Participants are advised to password-protect their phones if possible yet many do not have this option. We will therefore (a) never send messages with identifying information or directly refer to HIV or HIV treatment, and (b) only enroll YPLH who agree to the risk of game messages being seen by others who use their phone. Phone numbers and de-identified patient information is securely stored in a HIPAA- compliant cloud database hosted by Dimagi. Only select study staff will be able to link participant names with ID numbers. Information will be stored and destroyed following HIPAA and IRB procedures (see Protection of Human Subjects). Assessments: Assessments will take 1 hour to complete and be administered in a private room in the Clinic using ACASI at baseline and 6- and 12-months post-baseline. Clinic records will also be coded for biologic outcomes and clinic visits at these

assessments. Participants will be remunerated 40 Cedis (\$8) for each one. They will also be given 80 Cedis worth of prepaid phone credits to send and receive text messages at the baseline and first follow-up assessments.

Measures: The measures below will evaluate HIV-related health functioning, knowledge, attitudes, and behavior. Measures previously used in Ghanaian or SSA

adolescent or young adult samples were chosen when possible. If necessary, revisions to measures will be made based on formative work to ensure cultural relevancy. **Primary**

Outcomes: Past 30-day adherence will be assessed using a 3-item measure recently developed via intensive cognitive interviewing and field tests (47) and validated against electronic drug monitoring(48) . Self report of four day ART adherence based on percent of doses taken will also be assessed using the AACTG questionnaire (49). Staff will abstract from the clinic record number of medical visits kept and missed in the past 6 months(50), and most recent HIV viral load measurement, CD4 count, and current ART schedule. See Appendix 2 for data extraction form. If viral load was not measured in the past 3 months, it will be assessed at this visit as part of routine clinical care. **Secondary**

[figure not shown]
Outcomes: Figure 5 presents an assessment schedule for each aim and describes the secondary outcomes. Appendix 3 contains questionnaire.

Data Analytic Plan

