Appendix 2: Chart Review Data Abstraction Form

1) Today's date:
(MM)_____(DD)_____(YY)_____

2) Date of first presentation to KBTH:
(MM)_____(DD)_____(YY)_____

3) Age (years) _____

4) Gender
 1 – Male
 2 – Female

5) Marital Status
 1 – Single
 2 – Married
 3 – Divorced
 4 – Separated
 5 – Cohabiting
 6 – Not Available

6) Highest education level attained
 1 – None
 2 – Primary
 3 – JSS
 4 – MSLC
 5 – Sec/Tech
 6 – University

7) Employment/occupation at presentation

8) Employment status at presentation
 1 – Full time
 2 – Part time
 3 – On leave
 4 – Unemployed
 5 – Unknown

9) Dependent children (aged <18 years)
 1 – Total number

 2 – How many are HIV+

10) Funding type
 1 – Patient out-of-pocket
 2 – Medical insurance
 3 – Special project
 4 – Employer sponsored
 5 – Unknown
 6 – Other: _____

11) HIV status at presentation:
 Known positive
 Diagnosed at admission

12) Current WHO stage
 1 – Stage I
 2 – Stage II
 3 – Stage III
 4 – Stage IV

13) Current Drug Therapy (check all that apply):
 1 – Stavudine
 2 – Zidovudine
 3 – Lamivudine
 4 – Abacavir
 5 – Tenofovir
 6 – Didanosine
 7 – Nevirapine
 8 – Efavirenz
 9 – Combivir (zidovudine and lamivudine)
 10 – Kaletra (lopinavir/r)
 11 – Nelfinavir
 13 – Other:

14) Most recent CD4 cell count: _____

15) Date of most recent CD4 cell count test:

16) Most recent viral load: _____

17) Date of most recent viral load test:

18) Detectable viral load in past six months:
 – Yes
 – No

19) Date of ART initiation:
(MM)_____(DD)_____(YY)_____

20) Number of clinic appointments missed in the past 6 months

21) Number of clinic appointments kept in the past 6 months

22) Number of clinic appointments missed in the past 12 months

23) Number of clinic appointments kept in the past 12 months

24) Longest period without an appointment (months):

25) Route of HIV infection
 1 – Perinatal
 2 – Behavioral
 3 – Unknown

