Appendix 3: Questionnaire and Satisfaction Surveys

ALL QUESTIONNAIRE ITEMS WILL BE READ TO PARTICIPANTS AND ADMINISTERED BY A COMPUTER PROGRAM WITH RESEARCH STAFF PRESENT FOR ASSISTANCE.

Demographic Survey

Age	
Gender	1- Male 2- Female 3- Other
Ethnicity	1- Akan 2- Ga/Dangbe 3- Ewe 4- Northern Tribes 5- Multiple 6- Other
What language do you speak at home?	1- Twi/Fante/Bono 2- Ga/Dangbe 3- Hausa 4- Ewe 5- English 6- Other
Location of home	1- Kumasi 2- Outside of Kumasi
Distance traveled to Fevers Unit	1- 5km or less 2- 6-10km 3- 11-15km 4- 16-20km 5- 21-25km 6- 26-30km 7- 31-35km 8- 36-40km 9- 41km or more
Time to travel to Chest Clinic	1- less than 30 minutes 2- 30 minutes to 1 hour 3- 1-2 hours 4- more than 2 hours
How do you get to Chest clinic?	1- Public transportation 2- Walk 3- Private car 4- Other
How much does it cost you (GHS) to get to Chest clinic?	
Highest Education Completed	1- None 2- Primary 3- Secondary 4- Higher education

Currently in school	1- Yes, secondary (boarding school) 2- Yes, secondary (not boarding school) 3- Yes, higher education 4- No
Live with parents or caregivers	1- Yes 2- No
Parents died as a result of AIDS	1 - Yes, one parent 2 - Yes, two parents 3 - No
Does anyone else you live with have HIV?	1- Yes 2- No
Sexual orientation	1- Straight (heterosexual) 2- Gay or lesbian (homosexual) 3- Bisexual 4- Other
Marital status	1- Single/never married 2- Married 3- Divorced/separated 4- Widowed
Relationship status	1- In a relationship, living with partner 2- In a relationship, not living with partner 3- Not in a relationship
HIV status of partner	1- HIV positive 2- HIV negative 3- Not sure
Do you have children?	1- Yes 2- No
If yes, how many?	
Religion	1- No religion 2- Catholic/Anglican 3- Protestant 4- Other Christian 5- Muslim 6- Traditionalist/spiritualist 7- Other
Employment	1- Unemployed 2- Self-employed 3- Private or government employment
Monthly household income (GHS)	1- No income 2- 1-99 GHS per month 3- 100-199 GHS per month 4- 200-299 GHS per month 5- 300-399 GHS per month 6- 400-499 GHS per month 7- 500 GHS or more per month

How many people are in your household?	_____
Which of the following best describes the main dwelling where you live?	1. Formal dwelling (such as a house) 2. Informal dwelling (such as shack or tent)

Subjective Social Standing

Instructions – First Ladder

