5. I feel guilty because I have HIV _____
6. Having HIV in my body is disgusting to me _____
7. People I know would treat someone with HIV as an outcast _____
8. People I know would be uncomfortable around someone with HIV _____
9. People I know believe that a person with HIV is dirty _____
10. People I know would reject someone with HIV _____
11. People I know would not want someone with HIV around their children _____
12. People I know think that a person with HIV is disgusting _____

Concerns about Disclosure Tool

Questions and Filters	Response

Indicate your agreement or disagreement with each statement:
 
a) I am very careful who I tell that I have HIV. _____
 
b) I don't feel the need to hide the fact that I have HIV. _____
 
c) I worry that people may judge me when they learn I have HIV. _____
 
d) Telling someone I have HIV is risky. _____
 
e) Since learning I have HIV, I worry about people discriminating against me. _____
 
f) It is easier to avoid new friendships than worry about telling someone that I have HIV. _____
 
g) I work hard to keep my HIV a secret. _____
	
1 Strongly Disagree
 
2 Disagree
 
3 Agree
 
4 Strongly Agree

Past 30-Day ART Adherence

Instructions

1. In the last 30 days, on how many days did you miss at least one dose of any of your HIV medication?

Write in number of days: _____ (0-30)

2. In the last 30 days, how good a job did you do at taking your HIV medication in the way you were supposed to? Very poor Poor Fair Good Very good Excellent

3. In the last 30 days, how often did you take your HIV medication in the way you were supposed to? Never Rarely Sometimes Usually Almost always Always

Antiretroviral Adherence: ACTG

List the medications you take for HIV.

Study Drug Name/Dose	# Pills Each Time (Pills Each Dose)	# Times Per Day (Doses Per Day)

The next section of the questionnaire asks about the study medications that you may have missed taking over the last four days. Please complete the following table below.

**IF YOU TOOK ONLY A PORTION OF A DOSE ON ONE OR MORE OF THESE DAYS,
PLEASE REPORT THE DOSE(S) AS BEING MISSED.**

Step 1 Names of your anti-HIV study drugs	HOW MANY DOSES DID YOU MISS				
	Step 2 Yesterday	Step 3 Day before yesterday (2 days ago)	Step 4 3 days ago	Step 5 4 days ago	—
	• doses	• doses	• doses	• doses	
	• doses	• doses	• doses	• doses	

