C. Most anti-HIV medications need to be taken on a schedule, such as “2 times a day” or “3 times a day” or “every 8 hours.” How closely did you follow your specific schedule over the last four days?

Never	Some Of The Time	About Half Of The Time	Most Of The Time	All Of The Time
0	1	2	3	4

D. Do any of your anti-HIV medications have special instructions, such as “take with food” or “on an empty stomach” or “with plenty of fluids?” Yes ___ No ___

If Yes, how often did you follow those special instructions over the last four days?

Never	Some Of The Time	About Half Of The Time	Most Of The Time	All Of The Time
0	1	2	3	4

Some people find that they forget to take their pills on the weekend days. Did you miss any of your anti-HIV medications last weekend— last Saturday or Sunday? Yes ___ No ___

When was the last time you missed any of your medications? Check one.

- 5 Within the past week
- 4 1-2 weeks ago
- 3 2-4 weeks ago
- 2 1-3 months ago
- 1 More than 3 months ago
- 0 Never skip medications or not applicable

People may miss taking their medications for various reasons. Here is a list of possible reasons why you may miss taking your medications. How often have you missed taking your medications because you: (Circle one response for each question.)

	Never	Rarely	Sometimes	Often
1. Were away from home?	0	1	2	3
2. Were busy with other things?	0	1	2	3
3. Simply forgot?	0	1	2	3
4. Had too many pills to take?	0	1	2	3
5. Wanted to avoid side effects?	0	1	2	3
6. Did not want others to notice you taking medication?	0	1	2	3
7. Had a change in daily routine?	0	1	2	3
8. Felt like the drug was toxic/harmful?	0	1	2	3
9. Fell asleep/slept through dose time?	0	1	2	3
10. Felt sick or ill?	0	1	2	3
11. Felt depressed/overwhelmed?	0	1	2	3
12. Had problems taking pills at specified times (with meals, on empty stomach, etc.)?	0	1	2	3
13. Ran out of pills?	0	1	2	3
14. Felt good?	0	1	2	3

Antiretroviral Adherence: Visual Analog Scale

This measure of past 4-week antiretroviral adherence has been used in resource-limited settings in sub-Saharan Africa for patients with low literacy (Erb et al., 2017).

[figure not shown]

Figure 1: Pictogram-enhanced visual analog scale (VAS).

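### The four-day dose-count table behind a primary outcome still asks about study drugs although the trial has none, and other forms name sites and units other than the KATH HIV clinic

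*Combined protocol and SAP*

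**What the plan says.** The protocol's Measures section for the randomized pilot lists under Primary Outcomes: "Self report of four day ART adherence based on percent of doses taken will also be assessed using the AACTG questionnaire".

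The instrument is in Appendix 3, under Antiretroviral Adherence: ACTG. It begins "List the medications you take for HIV", above a regimen table whose first column is headed *Study Drug Name/Dose*. The missed-dose table follows. Its lead-in reads "The next section of the questionnaire asks about the study medications that you may have missed taking over the last four days", and its Step 1 column reads "Names of your anti-HIV study drugs". Later items drop the word *study*; one asks "Did you miss any of your anti-HIV medications last weekend".

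The trial has no investigational drug. Under Inclusion criteria, participants must already be receiving ART at the clinic, and "Study staff will NOT make changes to ART regimens". The arms are the text-message game and standard of care.

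The section on sample, site and recruitment gives the site as the HIV clinic at KATH in Kumasi. Item 2 of the chart form in Appendix 2 reads "Date of first presentation to KBTH". In the Demographic Survey of Appendix 3, one travel item reads "Distance traveled to Fevers Unit", while travel time, means of transport and cost are asked for the Chest Clinic. Item 12 of the locator form gives Korle-Bu as an example of how staff may identify themselves.

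**The concern.** The table appears to be carried over from a drug trial, where the study drugs and the participant's HIV drugs are the same thing. Here they are not. A participant who takes the words literally has no study medication, and may enter no missed doses or nothing at all. The first answer inflates the adherence score; the second leaves it uncomputable. Either would weaken one of the pilot's primary outcomes, and the Power paragraph already concedes that the pilot may be underpowered and hopes only for a signal.

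The site names raise a smaller, separate problem. If distance is reported for one place and time and cost for another, the travel items do not describe the same journey. The Literature Review counts travel cost and distance among the barriers to adherence, and a descriptive paper on the baseline sample is planned.

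**Working it through.** The plan states no figure on this point, so the check is mainly of wording, with one small calculation.

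**1. Which items can supply percent of doses taken?** The score needs doses prescribed and doses missed over four days.

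| Part of the ACTG section | Wording | Gives dose counts? |
|---|---|---|
| Opening line and regimen table | HIV medications in the instruction; study drug in the column head | Yes, doses per day (denominator) |
| Four-day table | Study medications; anti-HIV study drugs | Yes, doses missed (numerator) |
| Schedule item | Anti-HIV medications | No, a 0 to 4 rating |
| Weekend item | Anti-HIV medications | No, yes or no |
| Last missed dose | Your medications | No, time categories |

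Both components of the score sit under study-drug wording. The items with correct wording cannot replace them, because they give no counts.

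**2. How large is one wrong answer?** The plan prints no scoring formula. The natural one is

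score = 100 × (1 − missed doses / (4 × doses per day)).

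The documents do not give doses per day, so take one or two as assumptions:

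- One a day: 4 doses in four days; each unreported missed dose adds 100/4 = 25 points.
- Two a day: 8 doses in four days; each unreported missed dose adds 100/8 = 12.5 points.
- Extreme case: someone who listed their regimen, missed every dose and entered none scores 100 instead of 0.
- If no drug is listed, there is no denominator and no score.

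**3. How often would this happen?** The documents give nothing from which to estimate a rate.

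**4. Which other measures are touched?** The 30-day items and the visual analog scale both refer to HIV medication. Viral load and kept or missed visits are abstracted from the clinic record. None depends on the study-drug wording.

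**5. Site and unit names.** KATH is the stated site. KBTH (chart form), Korle-Bu (locator form), Fevers Unit (distance) and Chest Clinic (time, transport, cost) appear elsewhere. The documents do not expand KBTH, and do not say where either unit is. The Literature Review mentions a former research site, which is consistent with carried-over forms but does not prove it. What can be said from the text is that the names do not match KATH, and that distance is asked for a differently named unit from time and cost.

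**The case against.** The strongest reply is that context settles the meaning. The section is titled as antiretroviral adherence, its first instruction asks for the medicines taken for HIV, and the table itself says anti-HIV. A participant who has just written down their ART is likely to take study drugs to mean those medicines. The questionnaire is read out by computer with staff at hand, measures may be revised after formative work, and the third open-trial iteration uses the main measures before the pilot's procedures are settled.

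Much of this stands. A reader might infer that the whole questionnaire asks only about study medications. It does not; that is true of the four-day dose-count table alone. A reader might also infer that a literal reading scores as full adherence. That is not established: a participant who believes they have no study drug may leave the table blank. The plan has no rule scoring a blank as 100%, and it provides multiple imputation for missing data.

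The safeguards still do not correct the text. Someone who answers none because they take no study drug has no reason to ask for help, and the stated purpose of revising measures is cultural relevancy. On the site names, it is fair that no analysis names first-presentation date or travel distance as a covariate, and that staff abstracting KATH records may simply read KBTH as their own hospital.

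**Conclusion.** The point holds as a wording fault in the form that collects one primary outcome. The dose-count table refers to drugs the trial does not have, and this creates an avoidable risk of false zeros or unscorable tables. For an affected respondent the error could be 12.5 or 25 points per unreported dose, under the assumed regimens and the formula above. The share of respondents affected is unknown.

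Two stronger inferences are not supported. One is a stated loss of power: it would need a misreading rate and its effect on the variance, and the documents give neither. The other is bias in favour of one arm: the wording is the same in both, and nothing suggests that either would read it differently. The pilot's other adherence evidence is intact.

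The site and unit names are a separate, minor fault. It is certain that they are inconsistent. That the data would be recorded for a wrong place is only possible.

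**What to change.** In the four-day form of Appendix 3, replace every reference to study drugs or study medications, including the regimen column head, with *HIV medications (ART)*, in line with the 30-day measure. In item 2 of the Appendix 2 chart form, in all four travel items of the Demographic Survey and in item 12 of the locator form, use one correct name for the site and clinic, which by the protocol is the KATH HIV clinic.

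The cost is text edits to two appendices and the matching computer screens. Design, sample size and analysis do not change. If any assessments have already used the present wording, record the form version with each assessment so that the two sets can be told apart.
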